items 1 and 6 should only be used if applicable¹³. The teachers will give feedback on ways to improve performance and help the participants to set new learning goals and focus points for the continuous learning process. The feedback and teacher suggestions are uploaded to the participants individual channels on the online platform, allowing participants to consult these at a later stage in the learning process. While one participant is demonstrating the scan for the teacher using one of the scanners at the workshop, the remaining three participants will practice performing the scan and give each other feedback using the other ultrasound device. Following the first five workshops, there will be a short lecture for all participants, where the five new scanning modalities are explained and elaborated. After this the participants return to the workshops.

The next five workshop stations will introduce five new scanning modalities from the selected curriculum. At the workshop, a teacher will demonstrate the scanning modality according to the specific *actioncard*. The participants will then take turns explaining the performance of the scan and practice performing the POCUS examination on healthy volunteers (or phantoms for pelvic ultrasound). The teacher will assist and provide guidance.

After the second teaching seminar a post-self-quiz is available (a replication of the pre-self-quiz for teaching seminar 2) for the participants to create awareness about learning process and to illustrate to which extend the learning objectives of the first teaching seminar made been reached. The teachers will reach-out to participants, where the test scores reveal problems or difficulties, as well as participants, where the OSAUS score revealed specific difficulties. These participants will be offered additional support if needed.

In-between teaching seminar 2 and 3 (developing phase)

This phase in the learning process is considered and articulated as a developing phase, where participants continue to develop their scanning skills and routines. The participants are encouraged to use POCUS examinations on all patients with relevant clinical conditions suited for POCUS and to work with the integration of POCUS into their clinical practice and medical decision making. It is important in this phase that the participants develop routines and become comfortable performing POCUS examinations. During the eight weeks between the teaching seminars 2 and 3, participants are encouraged to register all POCUS examinations in their individual logbook in the online platform and note reflections and questions that occur during this process. The participants will still have the opportunity to consult the teachers during this phase by uploading questions, images or videos to the online platform. It is again recommended that participants perform a minimum of three POCUS examinations on patients within each scanning modalities during the eight weeks and that participants upload at least one POCUS examination of each of the five new scanning modalities for review and feed-back (assignments 8-12).

During the eight weeks, participants will be invited to participate in two half-an-hour webinars (on day 50 and 75). At these webinars, one of the teachers will go through some of the encountered problems and difficulties uploaded or posted on the online platform and present images and videos of common pathologies with the 10 selected POCUS modalities. Participants will also have the opportunity to ask questions and the teacher will have an ultrasound device and a volunteer available for live POCUS demonstration.

Before the third and final teaching seminar, the participants will be asked to complete a pre-self-quiz and to send in a list of questions or topics that they want included in the final teaching seminar (assignment 13).

[figure not shown]
Teaching seminar 3

Before the final teaching seminar, the teachers will prepare feedback for each participant based on the information gathered about each participant, i.e., from notes in the logbook, the uploaded scans, impressions from teaching seminars, the correspondence in the chat function, etc.

The structure of this final teaching seminar is similar to previous seminars. However, besides validating, adjusting and improving the participants' POCUS examinations, the goal is also to evaluate the participants' learning process, scanning competence and to offer guidance for future development.

Like the second seminar, this teaching seminar starts off with a plenum session where encountered experiences, problems or difficulties are shared and discussed. The teachers will address questions raised on the online platform and common difficulties identifies in the uploaded scans. The participants are invited to openly share and discuss. Afterwards, the participants are divided into small groups of 4 participants and they then circulate between hands-on workshop stations, as they did on the previous seminars. At the workshop stations, the participants will take turns demonstrating the POCUS scan for the teacher (figure 5). The teacher will then assess the participants' individual scanning competences using item 2-5 on the OSAUS score, give feedback on ways to improve performance and help the participants to set new learning goals and focus points for the continuous learning process. The participants will also receive suggestions for improvement from fellow participants, as the instructor invites to a discussion about the use of the scanning modality in general practice. The feedbacks and teacher suggestions are uploaded to the online platform, so participants may consult these at a later stage.

Figure 5. Structure of hands-on workshops on the third teaching seminar

At the end of the teaching seminar, participants will be asked to evaluate the educational intervention, their own learning outcome and to identify unanswered questions in the small groups. Afterwards, these are discussed in a final plenary session for all participants and teachers.

If needed, the teachers will upload additional information to the online platform to support the participants' further learning.

After the teaching seminar a final post-self-test is available (a replication of the pre-self-test for teaching seminar 3) for the participants to create awareness about continuous learning process and to illustrate to what extent the learning objectives of the teaching seminar have been reached. The teachers will reach out to participants, where the test scores reveal problems or difficulties, as well as participants, where the demonstration of the scan revealed specific difficulties. These participants will be offered additional support.

Competence assessment by experts

On the third teaching seminar, participants will have their scanning competence assessed by external experts. These experts are blinded to the participants previous experience and learning process. During the workshop rotation, each participant will step-a-side to have their competence assessed by a POCUS expert. This assessment will be staggered from the scanning modality being the topic of the workshop. Hence, the participants will first have the workshop with a specific scanning modality and then immediately after, during the next workshop, they will take turns, stepping-a-side for 10 minutes to have their scanning competence for the modality assessed.

The experts will assess the participants by asking the following questions:

- In which clinical scenarios would you perform this POCUS examination (Item 1 in the OSAUS)

The experts will ask participants to demonstrate the POCUS examination (for maximum five minutes) to assess the following:

- Applied knowledge of the ultrasound equipment (Item 2 in the OSAUS)
- Image optimisation (Item 3 in the OSAUS)
- Systematic examination (Item 4 in the OSAUS)
- Interpretation of images (Item 5 in the OSAUS)

The experts will present the participants with two picture of common pathology and ask the participants the following questions:

- How would you interpret these ultrasound findings? (Item 5 in the OSAUS)
- If you were to describe this examination in the medical record, what would you write? (Item 6 in the OSAUS)
- What would you do if you found it? (Item 7 in the OSAUS)

Immediately before each competence assessment by experts, participants will be asked to fill out a questionnaire where they declare whether or not they have POCUS scanning competence within this scanning modality to perform the scan un-supervised in general practice. The expert assessor are blinded to this declaration.

[figure not shown]
Participant commitment

The educational intervention requires considerable commitments from the participants (Figure 6). This will be outlined in both the course description, the introduction webinar and on the first teaching seminar. Participants will have to allocate three whole days for the teaching seminar and considerable time to practice scanning skills especially during the training phase (days 8-29). Furthermore, time will be allocated to perform assignments and follow the discussion on the online platform.

To ensure this commitment, time will be spent on building group relations on the first teaching seminar. In addition, a teacher will be allocated each participant as a mentor during the learning process. The mentor will monitor individual progress in the online platform and correspond with

the individual participant in the chat functions, provide feed-back on assignments and reach out to participants, who fail to be active on the online platform.

Figure 6. Overview of participant activities in the educational intervention

11b Criteria for discontinuing or modifying allocated interventions for a given trial participant

The trial may be discontinued for a GP in case of withdrawal of an informed consent. Hence, data collection will stop for that person at the time of withdrawal of the informed consent. Otherwise, this is an intention-to-treat study hence participants will not be excluded because of low adherence to the educational elements. However, we will collect data of the degree of participation for each participant.

11c Strategies to improve adherence to intervention protocols, and any procedures for monitoring adherence

The teacher will act as mentors for the participants and monitor participants' activity on the online platform. The teachers will monitor the activity of the participants, they are mentoring and reach out to participants, who fail to be active on the online platform or complete assignments. Reminders are sent to the GPs during the six months to remind them to register all POCUS examinations performed during clinical work.

11d Relevant concomitant care and interventions that are permitted or prohibited during the trial

The GPs are asked to refrain from seeking other POCUS education or courses during the study (months 1- 6). Still, information seeking e.g. through internet sources or books are allowed throughout the study.

12 Outcome measures

Primary outcomes:

The primary outcome is the Objective Structured Assessment of Ultrasound Skills (OSAUS) score scored after three (P1) and six months (P2).

The OSAUS assessment tool has been developed and validated as a generic tool for assessing scanning competence¹³. The OSAUS scale consists of seven items: ‘indication for the examination’, ‘applied knowledge of ultrasound equipment’, ‘image optimization’, ‘systematic examination’, ‘interpretation of images’, ‘documentation of the examination’ and ‘medical decision-making’ and each item is rated using a provided five-point Likert-scale with descriptions of performance ranging from very poor (score = 1) to excellent (score = 5). All items are weighted equally, as high inter-item correlation have been found previously¹⁴. Hence, for each scanning modality a total score from 7 to 35 points may be achieved.

(P1): The summarized OSAUS score after the educational period (three months after baseline) for all ten modalities will be calculated as percentage of maximum score and presented as median, IQR, minimum and maximum score.

(P2): The summarized OSAUS score after six months for all ten modalities will be calculated as percentage of maximum score and presented as median, IQR, minimum and maximum score.

Secondary outcomes

(S1). The total OSAUS score and the total items scores for each scanning modality included in the curriculum after the educational period (three months after baseline) will be calculated and presented as median, IQR, minimum and maximum score.

(S2). We calculate the proportion of GPs, who achieve a minimum OSAUS score of three for all seven domains for each of the ten scanning modalities after the educational period (three months after baseline). As variation in scores can occur between the four expert assessors. We will normalize the scores by multiplying a given assessors score with $(0.2 \times \text{sum of scores of all five assessors} / \text{the given assessors mean score})$ prior to calculating the proportion of successful GPs.

(S3): We calculate the proportion of GPs, who achieve a minimum OSAUS score of three for all seven domains for each of the ten scanning modalities after six months.

(S4): We calculate the proportion of GPs, who rate themselves as competent to perform POCUS un-supervised in general practice, after the educational period (three months after baseline), within each of the ten scanning modalities.

(S5): We calculate the proportion of GPs, who rate themselves as competent to perform POCUS un-supervised in general practice, after six months, within each of the ten scanning modalities.

Implementation process-related outcomes

(PR1): The GPs keep a log book of all scans they perform. The number of scans of the 10 modalities performed during months 1 to 3 and month 4 to 6 are summarized. Results are presented as the mean number of performed POCUS examinations by each GP during months 1 to 3 and during months 4 to 6.

(PR2): The number of adverse events and near-miss cases associated with the use of POCUS during months 1 to 6 will be summarized for each of the ten scanning modalities. Results will be presented as total numbers and frequencies.

(PR3): We will graphically evaluate the mean OSAUS score (y-axis) at the end of the educational intervention (3 months after baseline) as a function of each of the following educational aspects (x-axis).

- a. course days
- b. webinars,
- c. pre-and post-self-quizzes
- d. assignments (upload and feed-back)
- e. scans performed during the educational intervention

Background characteristics of participating GPs

At baseline the following participant characteristics will be collected: Age (years), gender (M, F, other), year of graduation from medical school, experience as a GP working in general practice (years), previous experience with ultrasound use (yes/no), previous training in ultrasound use (yes/no), scanner type (low range, mid range, high end), type of employment (practice owner/ employed/other), type of practice (collaboration, partnership, solo), location of practice (urban, rural, mixed), distance to nearest radiology department (km), number of patients assigned to the practice, number of GPs working in the practice will be presented.

13 Time schedule

Figure 7 Study timeline

Week	8	9	10	11	12	13	14	15	16	17	18	19	20	21	22	23	24	25	26	27	28	29	30	31	32	33	34	35
webinar																												
Teaching seminar																												
Skills assessment																												
Educational period																												
Transition period																												

Teaching seminars: Marts 3rd and 30th and June 9th 2022

Skills assessment: June 9th and September 1st 2022

Data collection educational period (months 1-3): Marts 3rd – June 9th 2022

Data collection after educational intervention (months 4-6): June 10th – September 1st 2022

14 Sample size

Our potential study population is 20 GPs who have signed up to participate in an ultrasound course organized by PLO-e. We expect a participation rate of 80% corresponding to 16 GP.

With 16 participants the total number of possible completed 7-item OSAUS questionnaires will be 16 for each modality and 160 for the combined estimate after 3 months and after 6 months. This is considered sufficient to estimate mean estimates and provide confidence intervals with acceptable spread.

15 Recruitment

Generally, to successfully change health care professionals' behaviours an intervention has to address motivation, capability, and opportunity³². From interviews with GPs not using POCUS (unpublished data) and a national survey²⁰, we have identified the following specific barriers to implementation of POCUS in general practice:

- cost of the ultrasound equipment
- lack of remuneration for performing POCOS,
- lack of education in the use of POCUS,
- lack of guidelines,
- high workload and time pressure in general practice.

This intervention was designed to take these potential barriers into account. From cohort studies conducted in Danish general practice we know that the time consumption for performing POCUS is below 10 minutes for the majority of novice POCUS users⁸ and with a median of 5 [IQR 3-8] minutes among experienced POCUS users¹⁰. However, we do not know if implementing POCUS in general practice overall increase or decrease work load.

Assignment of interventions

16a Allocation Sequence generation

n/a

16b Allocation concealment mechanism

n/a

16c Implementation

n/a

17 Blinding

Expert assessors performing the competence assessment (primary outcomes) have a medical background and are considered experts in the field. They will not be teaching participants in the training program. They will be blinded to the participants prior experience with POCUS, the number of performed POCUS examinations, and any other elements in the participants' learning process.

The researcher cleaning the data set and responsible for analyzing the primary outcome will have no knowledge of participants. He is a researcher with a physiotherapy background.

Data collection, management, and analysis

18a Data collection - Plans for assessment and collection of outcome, baseline, and other trial data

The OSAUS ultrasound competence assessment tool have been developed as a genetic tool to assess ultrasound competence across medical specialities. The assessment tool was developed through a Delphi study¹³ and it has been used to assess clinicians' ability to transfer learning from an ultrasonography course into diagnostic performance on patients¹¹. Furthermore, the tool has been found valid and reliable to distinguish between novice POCUS users and experts³⁴.

The OSAUS assessment tool measures competency according to seven key domains: 1) Indication for the examination 2) Applied knowledge of ultrasound equipment 3) Image optimization 4) Systematic examination 5) Interpretation of images 6) Documentation of examination and 7) Medical decision making. Each domain is rated using a five-point Likert scale with descriptions of performance ranging from very poor (score=1) to excellent (score=5).

Figure 8. The OSAUS competence assessment tool

	1	2	3	4	5
1. Indication for the examination					
If applicable. Reviewing patient history and knowing why the examination is indicated.	Displays poor knowledge of the indication for the examination		Displays some knowledge of the indication for the examination		Displays ample knowledge of the indication for the examination
2. Applied knowledge of ultrasound equipment					
Familiarity with the equipment and its functions, i.e. selecting probe, using buttons and application of gel.	Unable to operate equipment		Operates the equipment with some experience		Familiar with operating the equipment
3. Image optimization					
Consistently ensuring optimal image quality by adjusting gain, depth, focus, frequency etc.	Fails to optimize images		Competent image optimization but not done consistently		Consistent optimization of images
4. Systematic examination					
Consistently displaying systematic approach to the examination and presentation of relevant structures according to guidelines.	Unsystematic approach		Displays some systematic approach		Consistently displays systematic approach
5. Interpretation of images					
Recognition of image pattern and interpretation of findings.	Unable to interpret any findings		Does not consistently interpret findings correctly		Consistently interprets findings correctly
6. Documentation of examination					
Image recording and focused verbal/written documentation.	Does not document any images		Documents most relevant images		Consistently documents relevant images
7. Medical decision making					
If applicable. Ability to integrate scan results into the care of the patient and medical decision making.	Unable to integrate findings into medical decision making		Able to integrate findings into a clinical context		Consistent integration of findings into medical decision making

doi:10.1371/journal.pone.0057687.t003

From: Tolsgaard MG, Todsén T, Sørensen JL, Ringsted C, Lorentzen T, Ottesen B, et al. (2013) International Multispecialty Consensus on How to Evaluate Ultrasound Competence: A Delphi Consensus Survey. PLoS ONE 8(2): e57687. <https://doi.org/10.1371/journal.pone.0057687> (reference 13)

Education of POCUS expert assessors

The POCUS expert assessors all have prior experience using the OSAUS score. Still, prior to the assessment of the participants' performance in this study, the POCUS experts participate in a 90-minutes online training session with the principal investigator (CAA). During this training session, the POCUS experts are presented to the OSAUS score and the procedure for assessing the participants in this study. The POCUS experts are instructed to rate according to the standard expected from a GP, who is capable of performing POCUS unsupervised in general practice. During the training session, the POCUS experts will rate five POCUS videos individually and afterwards compare and discuss the results until agreement is reached. A similar training of POCUS raters has been reported in previous studies^{14,34}.

Self-rated scanning competence

Before the competence assessment by experts, the participants are asked to fill out a questionnaire, where they will declare whether or not they have the scanning competence to perform the given POCUS examination un-supervised in general practice.

Registration of performed POCUS examinations

The paper registration of clinical practice during patient consultations in general practice using APO registration sheets is a well-known and established method in Danish general practice³⁵. A paper logbook for participants will be developed as registration sheets for the participating GPs registration of POCUS use during the educational intervention (months 1-3 after baseline) and in the months following the intervention (months 4-6 after baseline). The registration sheets will be adapted versions of the sheets used in a previous APO studies⁸ (figure 9). This registration sheet has been used in a pilot study of the educational intervention (unpublished material).

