Secondary outcome 5 (S5): The proportion of GPs, participating in a POCUS training program with online support and three teaching sessions, who rate themselves to be competent to perform un-supervised POCUS in general practice, six months after baseline, for each of the ten scanning modalities included in the curriculum.

Implementation process related outcomes

Process-related outcome 1 (PR1): The number of performed POCUS examinations by each GP in the first six months after introducing POCUS use in general practice (months 1-6 after baseline).

Process-related outcome 2 (PR2): The number of adverse events and near-miss cases associated with the use of POCUS reported by the participating GPs in the first six months after introducing POCUS use in general practice (months 1-6 after baseline).

Process-related outcome 3 (PR3): The proportion of GPs, participating in a POCUS training program with online support and three teaching sessions, who have completed the different educational elements in the educational intervention three months after baseline.

8 Trial design

This is a hybrid effectiveness-implementation study¹⁵. We will test the effectiveness of an educational intervention in a real-world setting while gathering information on its delivery and the implementation of the intervention.

Reporting of this trial will follow STROBE guideline for reporting cohort studies¹⁶. Reporting of the protocol will follow the SPIRIT statement¹⁷. Before data collection starts, the trial will be registered on *clinicaltrials.gov*¹⁸.

Methods - Participants, interventions, and outcomes

9 Study settings

This study will be conducted in office-based general practice in Denmark with the educational sessions taking place at an ultrasound educational facility (MedSim, Central Denmark Region).

GPs in Denmark are self-employed and work in office-based general practice clinics. Denmark has a public health care system where almost all patients are listed with a GP for primary health care. Consultations and treatments are free-of-charge for patients. GPs act as gatekeepers for other primary care healthcare providers and secondary care specialists. GPs are paid through a combination of remuneration and fee-for-service financed through taxes. There is no fee for performing POCUS in primary care and GPs must cover expenses for the ultrasound device and their ultrasound education themselves.

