## 6. Implementation outcomes

(PR1): The GPs keep a log-book of all scans they perform. The number of scans of the 10 modalities performed during months 1 to 3 and month 4 to 6 are summarized. Results are presented as mean(sd) or median(IQR) number of performed POCUS examinations by each GP during months 1 to 3 and during months 4 to 6. Minimum and maximum score will also be presented.

(PR2): The number of adverse events and near-miss cases associated with the use of POCUS during months 1 to 6 will be summarized for each of the ten scanning modalities. Results will be presented as total numbers and frequencies.

(PR3): We will graphically evaluate the mean OSAUS score (y-axis) at the end of the educational intervention (3 months after baseline) as a function of each of the following educational aspects (x-axis): participation in the planned course activities (number of completed webinars and course days), number of completed pre-post quizzes, number of completed assignments, number of performed POCUS examinations.

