### *Adverse events and near-miss cases*

Adverse events (AE) and serious adverse events (SAE) related to or possibly related to the use of POCUS will be registered during all time after the training sessions.

At the teaching sessions, participating GPs will be taught how to report AE and SAE related or possibly related to the use of POCUS as well as near-miss cases. These events will be reported to the study adverse event committee in an online questionnaire specifically designed for this purpose. The participants will have a link for an online questionnaire in SurveyXact (Rambøll, Aarhus Denmark) where they will register: (1) Type of POCUS, (2) indication for the examination, (3) description of the event, (4) participant's reflections after the events and (5) questions for the adverse events committee.

The reporting of AE/SAEs to the study adverse event committee does not substitute or have any influence on the GPs responsibility to report adverse events to the Danish authorities (UTH anmeldelse). Such reporting will not be collected in this study.

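### PR1 and PR2 are defined for all POCUS use, but PR1 is counted, and PR2 broken down, only for the ten curriculum modalities

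*Protocol*

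**What the plan says.** Protocol 7 (and the registration data set in 2b) defines PR1 as "The number of performed POCUS examinations by each GP in the first six months after introducing POCUS use in general practice" and PR2 as "The number of adverse events and near-miss cases associated with the use of POCUS reported by the participating GPs" over the same six months. Neither definition mentions the curriculum. The secondary outcomes S1 to S5 in the same list do carry the limit, in the words "for each of the ten scanning modalities included in the curriculum".

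Protocol 12 then describes how each process outcome is summarised. PR1 is described as follows: "The GPs keep a log book of all scans they perform. The number of scans of the 10 modalities performed during months 1 to 3"; months 4 to 6 are handled likewise. For PR2, the events "will be summarized for each of the ten scanning modalities", and the results are then to be given as totals and frequencies. SAP 6 repeats both, with PR2 events "during months 1 to 6 will be summarized for each of the ten scanning modalities".

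Collection is wider than analysis. Reminders ask GPs to register every POCUS examination (Protocol 11c, SAP 3). GPs must report any event related or possibly related to POCUS (Protocol 22). The event form records "1) Type of POCUS, (2) indication for the examination, (3) description of the event" (SAP 7; also Protocol 18a).

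**The concern.** An outcome should be analysed with the scope in which it is defined. Here the definition covers all POCUS use and the analysis covers ten modalities, and no sentence connects the two. For PR1, consecutive sentences collect every scan and then count a subset, and Protocol 12 still labels the result as the number of POCUS examinations performed by each GP. For PR2, an event during a scan outside the ten has no row, and it is unclear whether it reaches the total.

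PR1 is the listed uptake outcome and PR2 the only listed safety outcome of a hybrid effectiveness-implementation study. Scanning beyond the taught scope is an implementation result in its own right, and the course gave no training for those scans. A reader of the paper would take the PR1 figure as all POCUS use and the PR2 figure as all POCUS-related events. The first would be wrong if any other scans took place, and the second might be.

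**Working it through.** The documents state no figure for this point, so there is nothing to reproduce. The check compares texts, followed by a range under stated assumptions.

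**Scope at each step**

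| Step | PR1 (scans) | PR2 (events) |
|---|---|---|
| Definition (Protocol 2b, 7) | all POCUS | all POCUS |
| Collection (Protocol 11c, 12, 18a, 22; SAP 3, 7) | all scans logged | any POCUS-related event, with type of POCUS |
| Analysis (Protocol 12, SAP 6) | ten modalities | broken down by ten modalities; scope of the total not stated |

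For PR1 the narrowing is explicit. For PR2 the breakdown is narrower than the definition, and the total can be read either way.

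**A second scan count.** PR3 plots OSAUS against the number of scans performed in the educational period, with no ten-modality limit (Protocol 12, SAP 6). The paper could therefore show two different scan counts under nearly the same name.

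**Possible size.** Let q be the share of scans outside the curriculum, and r the event rate per such scan relative to a curriculum scan. The documents give neither, so the values below are assumptions.

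- Undercount in PR1 = q.
- Share of events missing from PR2, if its total covers only the ten modalities = rq / ((1 − q) + rq). Example with q = 0.20 and r = 2: 0.40 / (0.80 + 0.40) = 0.33.

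| q | PR1 undercount | PR2 missed, r = 1 | r = 2 | r = 3 |
|---|---|---|---|---|
| 5% | 5% | 5% | 10% | 14% |
| 10% | 10% | 10% | 18% | 25% |
| 20% | 20% | 20% | 33% | 43% |
| 30% | 30% | 30% | 46% | 56% |

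**Frequencies.** The denominator of the PR2 frequency is not stated. If the numerator is all events and the denominator is the ten-modality PR1 count, the rate per scan is inflated by 1 / (1 − q): 1 / 0.90 = 1.11 at q = 10%, and 1 / 0.80 = 1.25 at q = 20%. So reading the PR2 total as all events does not remove the problem, because the scopes of numerator and denominator may then differ.

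**The case against.** A reader might infer that harm from off-curriculum scans drops out of the trial's safety outcome. The documents do not support that as a fact. After the modality breakdown, PR2 is to be presented as totals, and these may cover every reported event. No sentence excludes an event from another scan. Whatever PR2 reports, such events are collected with their type and go to a safety committee that handles every report (Protocol 5d, SAP 9) and can end the trial (SAP 9). The possible loss is in the reported outcome, not in collection or oversight. This stands.

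A reader might also infer that such scans vanish from the only count of POCUS use. PR3 carries a scan count without the limit, although only as a plotting variable and only for the educational period.

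A further defence is that Protocol 12 is the operational definition of a short-form objective. Counting uptake of the ten taught modalities is coherent for a ten-modality course, and narrowing the wording in Protocol 2b and 7 would also close the gap. That is fair for PR1. For PR2, narrowing would leave reported events outside the outcome unless they were listed separately.

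Finally, the documents do not show that off-curriculum scanning is common. The ten were chosen as frequently met in general practice, and GPs are said to start with a few curriculum scans. Against that, earlier POCUS users are eligible, SAP 4 tabulates POCUS experience, and the developing phase encourages scanning wherever a condition suits POCUS, with no stated limit to the curriculum. Such scans are plausible but not quantified.

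**Conclusion.** The mismatch is real and appears in both documents. PR1, followed as written, does not deliver its defined count if any scan falls outside the ten modalities. PR2 has no row for an event from such a scan and may under-report; whether it does depends on how its total is read.

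The size is unknown. The tabulated percentages follow from the assumed q and r, and those for PR2 also assume that its total covers the ten modalities only. They show how the loss scales and estimate nothing about this trial.

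The effect is confined to two descriptive process outcomes in a single-group study that expects about 16 of 20 invited GPs. No test or decision rule rests on them, and P1 and P2 are untouched. The change is still worth making, because it brings both outcomes into line with their definitions and removes a possible under-report from the one listed safety outcome at almost no cost.

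**What to change.** In Protocol 12 and SAP 6:

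- Report an all-POCUS total for scans (PR1) and for events and near-misses (PR2).
- Break each total down by the ten modalities plus a row for *other POCUS (outside the curriculum)*.
- Keep the ten-modality scan count, labelled as curriculum uptake.
- Give any PR2 frequency with the same scope in numerator and denominator, and name the denominator.
- State whether the scan count in PR3 is the all-POCUS or the ten-modality figure.

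The registration sheet (Protocol 18a, Figure 9) cannot be read in the copy available, so it is not known whether it has a field for other scans. SAP 13 shows that data analysis had begun, so a change to the sheet would come too late and only reporting can change. If the sheet did not capture other scans, label PR1 as curriculum scans only, and still report all POCUS-related events in PR2, since the event form records the type of POCUS.

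The cost is a few words in two sections, one extra row per table, and possibly a slightly less favourable event count.
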